6.2.3. Other therapies allowed

Any concomitant medication that the participant receives during the participation in this study will also be recorded (see Sections 5.4.1 and 6.2.2.). Specifically, dose, posology, frequency of administration, start and end date and reason of use will be required and collected.

As for SmPC the following medications are not allowed as concomitant medications: cholestyramine (or any ion exchange resin), medications used in treatment of early or advanced breast cancer (including adjuvant therapy), any antiretroviral medication, warfarin or other coumarin derivatives (the combination with raloxifene may cause modest decreases in the prothrombin time).

6.2.4. Safety monitoring and individual stopping rules

Safety data to be recorded:

- vital signs: blood pressure (systolic and diastolic) and heart rate will be measured daily the patient him/herself using an electronic device. BP and HR measurements will be done with the subject comfortably seated on a chair, with the middle of the cuff on the upper arm at the level of the right atrium (the midpoint of the sternum). Also the body temperature will be measured by 10:00 am using an electronic device.
- SpO₂ will be measured by transdermal oximetry to be collected once daily concomitantly with the BP / HR measurement.
- laboratory tests will be performed on venous blood samples taken from the patient at domicile (drawings performed by a nurse sent to the patient's domicile and delivered to the study site's laboratory). The lab results should be reviewed by the Investigator and clinically relevant changes recorded as AEs. Training to the personell in charge of the samples collection and delivering to the laboratory, and instructions to the laboratory personnel for reporting the lab assessments will be performed at the initial site visit.

Any sign or symptom associated to adverse events will be reported by the patient in an electronic patient diary EXOM GENIUS ROSA and reported during the telemedicine consult. The eDiary should be filled in daily by the patient by 09:00 pm.

All patients will be withdrawn from the study when criteria for supplemental oxygen therapy and/or mechanical ventilation are met. Another stopping rule (patient's withdrawal from study) includes drug related adverse events grade ≥ 3 according to Common Terminology Criteria for Adverse Events (CTCAE) version 5.0 [Common Terminology Criteria for Adverse Events (CTCAE) Last Updated: 03/01/18 available at https://ctep.cancer.gov/protocolDevelopment/electronic_applications/ctc.htm]

Patients are free to withdraw from participation in the study at any time upon request, without any consequence. Patients should be listed as having withdrawn consent only when they no longer wish to participate in the study and no longer authorize the Investigators to make efforts to continue to obtain their outcome data. Every effort should be made to encourage patients to remain in the study for the

duration of their planned outcome assessments. Patients should be educated on the continued scientific importance of their data, even if they discontinue the study. In the case of a patients becoming lost to follow-up, attempts to contact the patient should be made and documented in the patient's medical records.

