3.3. OVERALL STUDY DESIGN

This clinical study will be a multicenter, adaptive, double-blind, randomized, placebo controlled, parallel-group, to study efficacy and safety, with the following adaptive components:

- Parallel multi-arms (2 interventional arms and 1 placebo control arm);
- A 2-stage sequential design (1 interim analyses + 1 final analysis);
- Sample size re-calculation at interim stage;
- Stopping rule for efficacy or futility at interim stage.

The study will be a total of 5 weeks in duration: a screening period of 7 days, followed by 2 weeks of double-blind treatment and a 2-week follow-up period. At the end of the screening period, patients meeting the entry criteria for this study will be randomized (1:1:1) to 1 of 3 treatment groups (group 1, group 2 or group 3) and instructed by a physician on the correct self-administration of the treatment and completion of the patient diaries.

After an administration of two oral doses in the first day of treatment (one dose in the morning and one dose in the evening, each dose administered with 2 capsules containing 60 mg of the active substance or placebo), a single daily oral dose of raloxifene (60 mg Group 1, 120 mg Group 2 – treatment groups) or placebo (Group 3 - control group) will be taken on by the patients for two weeks.

Treatment groups:

- Group 1: will receive one capsule of raloxifene 60 mg and 1 capsule of placebo.
- Group 2: will receive two capsules of raloxifene 60 mg.

Control group:

- Group 3: will receive two capsules of placebo.

Following the completion of the double-blind treatment or premature discontinuation during the double-blind phase, patients will be followed up for safety assessments until the planned last study visit. In case of early treatment termination an End of Follow Up will be sought at the same timepoint.

3.3.1. Rationale for Selection of dose, control group and treatment schedule in the study

A double-blind study design was adopted to minimize systematic bias. Randomization is expected to minimize patient selection bias and increase baseline comparability between treatment groups. The use of placebo control is critical to the study design for, providing an accurate estimate of the additive benefit of pharmacotherapy.

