In case of discontinuation, subjects will undergo a remote Early Trial Discontinuation Visit aimed to assess physical abnormalities, vital signs and transdermal oxygen saturation measurement.

Replacement Procedures

No patient who has been randomized and withdraws from the study for any reason will be replaced.

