7.3 EARLY WITHDRAWAL FROM THERAPY OR ASSESSMENT AND END OF STUDY

7.3.1 EARLY TRIAL DISCONTINUATION VISIT AND UNSCHEDULED VISITS

In general, for by-visit summaries, data recorded at the nominal visit will be presented.

Unscheduled measurements will not be included in by-visit summaries. Listings will include scheduled, unscheduled, and early trial discontinuation visit (ETDV).

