14 ANALYSES OF EFFICACY VARIABLES

14.1 EFFICACY ANALYSES

NEWS score evaluation will be performed at T0, T7, T14 and T28. NEWS score and NEWS score parameters as per collected in CRF will be provided in Listing for FAS population. Refer Appendix 3 for NEWS score.

Table 3: Summary of Analyses Strategies for efficacy endpoints:

Endpoint	Analysis set	Statistical method	Factors/Co variates	Missing data Handling	Analyses type
Virologic outcome - Proportion of patients with undetectable SARS-CoV-2 at PCR at day 7 after randomization.	FAS	Binary Logistic regression	Treatment, center, age and status	Missing data will not be imputed	Primary analysis
Virologic outcome - Proportion of patients with undetectable SARS-CoV-2 at PCR at day 7 after randomization.	PP	Binary Logistic regression	Treatment, center, age and status	Missing data will not be imputed	Sensitivity analysis
Clinical outcome - Proportion of patients who does not require supplemental oxygen therapy (NEWS ≤2) and/or mechanical ventilation at day 14 after randomization.	FAS	Binary Logistic regression	Treatment, center, age, status and baseline NEWS	Missing data will not be imputed	Primary analysis
Clinical outcome - Proportion of patients who does not require supplemental oxygen therapy (NEWS ≤2) and/or mechanical ventilation at day 14 after randomization.	PP	Binary Logistic regression	Treatment, center, age, status and baseline NEWS	Missing data will not be imputed	Sensitivity analysis

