14.1.1 PRIMARY EFFICACY ENDPOINTS AND ANALYSES

1. Proportion of patients with undetectable SARS-CoV-2 at PCR at day 7 after randomization (virologic endpoint). This endpoint will be derived as below.
 - Based on Approved molecular test (PCR) result at day 7, the responses will be considered as “detectable” if PCR result is “Positive” otherwise “undetectable” if PCR result is “Negative” (Missing PCR result will be considered as missing in the main analysis).

The response (detectable / undetectable) at day 7 will be analysed using Binary logistic regression model with treatment group and pre-defined baseline factors (center, age, status and their interaction effects with treatment group). Odds ratio

will be computed for comparisons of each active treatment group versus placebo. i.e., raloxifene (60 mg) versus placebo and raloxifene (120 mg) versus placebo.

2. The proportion of patients who does not require supplemental oxygen therapy (NEWS ≤ 2) and mechanical ventilation at day 14 after randomization (clinical endpoint). This endpoint will be derived as below.

- If collected NEWS score > 2 or mechanical ventilation at day 14 result “Yes” then the response will be considered as “Required”. If collected NEWS score ≤ 2 and mechanical ventilation with result “No” then the response will be considered as “Not Required” (if both NEWS score and mechanical ventilation are missing, patient will be considered as missing).

The response (Required/ Not required) at day 14 will be analysed using Binary logistic regression model with treatment group and pre-defined baseline factors (center, age, status, baseline NEWS and their interaction effects with treatment group). Odds ratio will be computed for comparisons of each active treatment group versus placebo. i.e., raloxifene (60 mg) versus placebo; and raloxifene (120 mg) versus placebo.

For both virologic and clinical endpoint, Binary Logistic regression will be performed using PROC GENMOD in SAS® on the observed data only to estimate difference in proportions between each active treatment versus placebo and its corresponding 95% (2-sided) confidence intervals. Exponential transformation will be used to obtain the odds ratio and corresponding 95% confidence interval. P-values will be reported based on the Wald tests from Type III analyses. Bonferroni method will be considered to handle multiple treatment comparisons.

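### The clinical primary analysis drops, instead of counting as failures, patients who die before day 14 and patients withdrawn for oxygen or ventilation criteria who have no day-14 record

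*Protocol*

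**What the plan says.** **Withdrawal.** Protocol 6.2.4: "All patients will be withdrawn from the study when criteria for supplemental oxygen therapy and/or mechanical ventilation are met". The premature-discontinuation list in Protocol 6.3 also includes documented disease progression among the reasons for leaving the study.

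**Follow-up.** Other text points the other way. Protocol 3.3 says that after completion or premature discontinuation of treatment "patients will be followed up for safety assessments until the planned last study visit". Protocol 6.2.4 adds: "Patients should be educated on the continued scientific importance of their data, even if they discontinue the study". Protocol 6.3 keeps patients who stop the study drug under observation for efficacy and safety. SAP 7.3.2 lists disease progression as a reason for stopping treatment but not for leaving the study.

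**Scoring.** Under SAP 14.1.1 a patient is 'Required' (failure) if day-14 NEWS exceeds 2 or ventilation is 'Yes', and 'Not Required' if NEWS is at most 2 and ventilation is 'No'. Otherwise, "if both NEWS score and mechanical ventilation are missing, patient will be considered as missing". The analysis is then specified: "Binary Logistic regression will be performed using PROC GENMOD in SAS® on the observed data only". SAP Table 3 confirms: "Missing data will not be imputed". Neither place mentions death or withdrawal.

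**Discontinuation visit.** Protocol 6.3 describes it as "aimed to assess physical abnormalities, vital signs and transdermal oxygen saturation measurement". Oxygen and ventilation status are not among those aims. SAP 7.3.1 uses nominal-visit data for by-visit summaries and names this visit only for listings. No rule carries it into day 14.

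**Sensitivity.** Protocol 9.5.2.1 leaves to the SAP the sensitivity analyses for missing data and for protocol deviations. SAP 8.3 contains only a per-protocol analysis on observed data.

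**The concern.** The clinical endpoint asks whether the patient is free of oxygen or ventilation need at day 14. Death is the plainest failure on that question, yet a patient who dies before day 14 has neither component recorded and leaves the analysis. A patient withdrawn because of oxygen or ventilation criteria can leave by the same route. In both cases the reason for the missing record is related to the outcome, so an observed-data analysis is not neutral.

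At stake are inflated success rates in every arm that loses failures, some loss of precision and, if the loss differs between arms, a biased treatment effect. The protocol's statement in 9.4 that the full analysis set is analysed by allocation regardless of intercurrent events does not cure this. It fixes who belongs to the set and in which arm, but assigns nobody an outcome.

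**Working it through.** **1. The plan's own figures.** Inputs: one-sided alpha 0.025 and Bonferroni over two endpoints and two doses (Protocol 9.1), so 0.025/4 = 0.00625. The Pocock constant for two equally spaced looks at 0.00625 is 2.6964, matching the 2.69640 in Protocol 9.3, Table 1. With 50 per arm at the interim as half the plan, the planned size is 100 per arm. Two looks at 2.6964 with rates of 50% and 75% give about 85% power for one clinical comparison in simulation (non-binding futility), consistent with the stated aim of more than 80%.

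**2. Model of the gap.** Let s be the true success rate and f the share of failures with no day-14 record. The documents give no value of f, so it is an assumption. I show 0 to 0.25.

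- Observed success = s / (s + (1 − s)(1 − f)).
- Observed odds ratio = true odds ratio × (1 − f_placebo)/(1 − f_active).
- SE(log OR) = square root of the sum of 1/expected cell, with cells n·s and n(1 − s)(1 − f) in each arm.
- Power per comparison = Φ(ln 3/SE − Z), unadjusted for covariates.

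**3. Equal loss.** The true odds ratio is (0.75/0.25)/(0.50/0.50) = 3.0, and it stays 3.0. SAP 4.3 reports 68 patients; an equal split is assumed, 68/3 ≈ 23 per arm. With no interim analysis, Z = Φ⁻¹(1 − 0.00625) = 2.498. Failures lost per comparison = f × 23 × (0.50 + 0.25).

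| f | Observed success, placebo / active | Difference (points) | Failures lost (of 17.25) | SE, 23/arm | Power, 23/arm | Power, 100/arm (Z = 2.6964) |
|---|---|---|---|---|---|---|
| 0 | 50.0% / 75.0% | 25.0 | 0 | 0.637 | 22.0% | 81.6% |
| 0.10 | 52.6% / 76.9% | 24.3 | 1.7 | 0.659 | 20.3% | 78.2% |
| 0.25 | 57.1% / 80.0% | 22.9 | 4.3 | 0.702 | 17.6% | 71.5% |

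Example, f = 0.10 at 23 per arm: SE = √(1/11.5 + 1/10.35 + 1/17.25 + 1/5.175) = 0.659; ln 3/0.659 − 2.498 = −0.83; Φ = 20.3%.

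The 100-per-arm column is a single test at Z = 2.6964 and describes the trial as planned, not the one that stopped at 68. If the final fallback in SAP 14.1.1, Fisher's exact test, is reached, exact power at 23 per arm and one-sided 0.00625 is 14.0%, 13.3% and 10.9% for the same three values of f. The fallbacks use the same observed data and restore no lost failure.

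**4. Unequal loss, in whole patients at 23 per arm.** Take placebo 12 successes and 11 failures, active 17 and 6.

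- Nothing lost: (17/6)/(12/11) = 2.60.
- Two active failures lost, none on placebo: (17/4)/(12/11) = 3.90.
- Two placebo failures lost, none on active: (17/6)/(12/9) = 2.13.

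These show sensitivity; they do not predict which way any loss would go.

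**The case against.** The strongest reply is that these patients are probably followed. Besides the passages above, SAP 14.1.2 analyses time to relief from oxygen or ventilation. Entry criteria exclude anyone who needs either, so that outcome presupposes follow-up after the need arises. ICU admission, hospitalisation and survival are endpoints at days 7, 14 and 28. This stands: it makes a large f hard to support, and it may mean that 6.2.4 is mainly loosely worded. It does not close the gap. The instruction in 6.2.4 and the study-discontinuation reason in 6.3 remain, and follow-up cannot give a day-14 NEWS to a patient who died earlier.

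A reader might also infer that the withdrawal trigger is itself the endpoint failure, so that most failures are removed by design. The documents do not support that. The scored failure is NEWS above 2 or ventilation at day 14. NEWS can exceed 2 through temperature, pulse, blood pressure or respiratory rate without oxygen, and a patient who met oxygen criteria on day 5 may have recovered by day 14. The two events are related but not identical.

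Finally, the size depends on the multiplicity reading. SAP 8.4 covers endpoints and treatments, giving four comparisons; SAP 14.1.1 names only treatment comparisons. With two, Z = 2.241 and power at 23 per arm is 30.3%, 28.3% and 24.9% for f = 0, 0.10 and 0.25. The level changes, but the pattern does not.

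**Conclusion.** The point holds in this limited form. Followed as written, the SAP excludes a death before day 14 from the clinical primary analysis. It does the same to a patient withdrawn for oxygen or ventilation criteria who has no day-14 record. The missing-data sensitivity analysis deferred to the SAP is absent, and SAP section 18 does not list its omission as a change.

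The size is uncertain and may be small. Equal loss costs about 2 to 4 percentage points of power at 23 per arm for f = 0.10 to 0.25, and the low starting power is mainly due to early termination. Bias in the odds ratio requires unequal loss. With so few failures, two patients are enough to matter. A reader might infer that the analysis favours raloxifene; nothing in the documents shows which arm would lose more failures, so no direction can be claimed.

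The figures assume the protocol's 50% and 75% rates, an equal split of 68 patients, four-way Bonferroni and assumed values of f. The gap itself rests on the text and needs none of these. It should be fixed before unblinding, because a scoring rule chosen afterwards would be open to challenge.

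**What to change.** Before unblinding:

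1. In SAP 14.1.1, score death on or before day 14 as 'Required'.
2. For living patients withdrawn for oxygen or ventilation criteria, first retrieve day-14 status from the eCRF and from oxygen, ventilation, ICU and hospitalisation records. Score 'Required' only if it cannot be recovered. SAE records alone are not enough, because Protocol 8.4.3 keeps trial endpoints out of SAE reporting.
3. Add a supportive analysis that counts any oxygen or ventilation need, or death, through day 14 as failure for every patient, whether or not a day-14 record exists. Step 2 alone would treat two patients with the same course differently according to record availability. The uniform version also matches the objective in SAP 3.1.1, which is worded as within 14 days.
4. Add the sensitivity analysis promised in Protocol 9.5.2.1, worst-case or tipping-point, for patients whose status is truly unknown. Log all of these changes in SAP section 18.
5. Reconcile Protocol 6.2.4, Protocol 6.3 and SAP 7.3.2 on whether outcomes are collected after these criteria are met. No stopping rule is proposed here.

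Cost: a short derivation rule, two extra tables and a section 18 entry. The eCRF is not visible, so some data queries may be needed. Observed success rates will look less favourable.

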In case of discontinuation, subjects will undergo a remote Early Trial Discontinuation Visit aimed to assess physical abnormalities, vital signs and transdermal oxygen saturation measurement.

Replacement Procedures

No patient who has been randomized and withdraws from the study for any reason will be replaced.

6.4. END OF STUDY (EOS)

The EOS is defined as the last day the last patient completes the last study assessment, or retracts the consent to participate in the study, or withdraws from the study, or is deceased or otherwise lost to follow-up.

7. ENDPOINTS

7.1. STUDY ENDPOINTS

7.1.1. Primary endpoints

Virologic outcome. Proportion of participants with undetectable SARS-CoV-2 at PCR at day 7 after randomization.

Clinical outcome. Proportion of participants who not requires supplemental oxygen therapy (NEWS ≤ 2) and/or mechanical ventilation at day 14 after randomization.

7.1.2. Secondary endpoints

- Proportion of participants with undetectable SARS-CoV-2 at PCR at day 14 after randomization at day 28 after randomization;
- Proportion of participants who does not require supplemental oxygen therapy (NEWS ≤ 2) and/or mechanical ventilation at day 7 and 28 after randomization;
- Proportion of patients in each NEWS category at time 7, 14 and 28 after randomization;
- Mean value of NEWS category at time 7, 14 and 28 after randomization;
- Proportion of participants with any adverse event with grade ≤ 2 according to CTCAE at day 7, 14 and 28 after randomization;
- Proportion of participants with any severe adverse events (grade ≥ 3 according to CTCAE) at day 7, 14 and 28 after randomization;
- Proportion of hospitalized participants who at the beginning of the study were at domicile isolation at day 7, 14 and 28 after randomization;
- Proportion of participants admitted to intensive care at day 7, 14 and 28 after randomization;
- Proportion of survivors at day 7, 14 and 28 after randomization;
- Mean variation of value of the following biomarker parameters, from base line to day 7, 14, 21 and 28 after randomization:
 - Complete blood cell counts;
 - Hepatic function (ALT, AST and bilirubin);
 - Coagulation (PT, aPTT and INR);
 - Other marker including (D-dimer, CPK, LDH);
- Quality of life questionnaire 3 months after the randomization.

8. EVALUATION OF ADVERSE EVENTS AND SAFETY INFORMATION

8.1. DEFINITIONS

Adverse Event

An **Adverse Event (AE)** is defined as any untoward medical occurrence in a patient or clinical investigation subject administered a medicinal product and which does not necessarily have a causal relationship with this treatment. An AE can therefore be any unfavourable and unintended sign (including an abnormal laboratory finding), symptom, or disease temporally associated with the use of a medicinal product, whether or not related to the medicinal product.

Adverse Drug Reaction

An **Adverse Drug Reaction (ADR)** is defined as an adverse experience which is a reasonably likely to have been caused by the drug. Adverse events are to be considered unsuspected if the relationship to the study drug as described in the table in section 8.2.1 is none or unlikely; whereas any AE reported in the study having a possible, probable or highly probable relationship to study drug will be considered as an ADR. The definition covers also medication errors and uses outside what is foreseen in the protocol, including misuse and abuse of the product.

Serious Adverse Event

A **Serious Adverse Event (SAE)** is defined as any untoward medical occurrence that at any dose:

- results in death,
- is life-threatening (i.e. the patient was at risk of death at the time of the event. It does not refer to an event which hypothetically might have caused death if it were more severe),
- requires inpatient hospitalization or prolongation of existing hospitalization,

NOTE: In general, hospitalization means that the individual remained at the hospital or emergency ward for observation and/or treatment (usually involving an overnight stay) that would not have been appropriate in the physician's office or an out-patient setting. Complications that occur during hospitalization are AEs. If a complication prolongs hospitalization or fulfills any other serious criteria, the event is serious. When in doubt as to whether "hospitalization" occurred, the event should be considered serious.

- results in persistent or significant disability/incapacity,

NOTE: This definition is not intended to include experiences of relatively minor medical significance such as uncomplicated headache, nausea, vomiting, diarrhea, influenza, or accidental trauma (e.g., sprained ankle) which may interfere or prevent everyday life functions, but do not constitute a substantial disruption.

- is a congenital anomaly/birth defect,
- is medically significant or important medical condition, i.e. an important medical event that based upon appropriate medical judgment, may jeopardize the patient and may require medical or surgical intervention to prevent one of the outcomes listed above.

An important medical condition is an event that may not result in death, be life-threatening, or require hospitalization but may be considered a SAE when, based upon appropriate medical judgment, it may jeopardize the patient and may require medical or surgical intervention to prevent one of the outcomes listed above. Examples of such medical events include allergic bronchospasm requiring intensive treatment in an emergency room or at home, blood dyscrasias or convulsions that do not result in patient hospitalization, or the development of drug dependency or drug abuse.

Pre-planned hospitalization or hospitalization for routine treatment or monitoring of the studied indication, not associated with any deterioration in condition are not considered to be SAEs (see Par. 8.3.2).

These events must be recorded in the AE page of the eCRF where a variable will be ticked to indicate that they are not SAEs.

Death shall always be reported as SAE and the cause of death shall always be specified when known. Death due to progression of disease may be unrelated to study treatment and causality shall be assessed by the Investigator. The investigator should report the event immediately to the sponsor and the sponsor shall comply with regulatory reporting, unless there is no reasonable possibility that the drug may have caused the fatal outcome of the disease progression.

Expectedness

Despite raloxifene has been on the market for many years with an authorised Summary of Product Characteristics, considering that this trial is investigating raloxifene in a new condition and patient population, all events (AE and SAE) will be assessed as unexpected by the Sponsor. The authorised SmPC may be considered the reference document for safety information, but shall not be used for the evaluation of the expectedness.

Suspected serious unexpected adverse reaction (SUSAR)

A suspected serious unexpected adverse reaction is defined as an adverse reaction that is both unexpected (not consistent with the applicable product information) and also meets the definition of a Serious Adverse Reaction.

Adverse event of special interest (AESI)

An adverse event of special interest (serious or non-serious) is an event thought to be [potentially] associated with the investigational compound or disease under study and for which close monitoring is advised. Reporting on Adverse Events of Special Interest is an emerging and ever more critical aspect related to characterizing the safety profile of a compound, for which ongoing monitoring and communication by the investigator to the sponsor as SAE is requested.

